1.3 Schedule of Activities

Part 1

Observation/test timing	Pre-screening	Screening test	Registration	Baseline	Week 1	Week 2	Week 3	Week 4	Week 5	Discontinuation
Visit window	-	28 days before Day 1 (Day -28) to Day -7	-	Day -2 to Day 1	Day 1	Day 8 to Day 11	Day 15 to Day 18	Day 22 to Day 25	Day 29 to Day 32	Within 28 days from discontinuation
JR-171 administration					Х	Χ	Х	Χ		
Informed consent	X									
Subject baseline characteristics ^{a)}		Х								
Assessment based on			Х							
inclusion/exclusion criteria			^							
Pregnancy testing (female subjects of childbearing potential only)		X								
Vital signs ^{b)}		Xc)		X _d)	X ^{e)}	X ^{e)}	X ^{e)}	X ^{e)}	X ^{c), f)}	X _{c)}
Laboratory tests ^{f)}		X		X		X	X	X	X	X
Antibodies ^{f)}				X ^{g)}		X ^{h)}			X ^{g)}	X ^{g)}
Plasma drug concentration ⁱ⁾					Х	X	Х	Х		
Drug concentration in CSF				X ^{f)}				X ^{j)}		X ^{k)}
HS and DS concentrations in CSF				X ^{f)}				X ^{j)}		X ^{k)}
CSF opening pressure				X ^{f)}				X _{j)}		X ^{k)}
Urinary HS and DS concentrations (including measurement of creatinine for concentration adjustment) ⁽⁾				х		Х	Х	Х	Х	х
Serum HS and DS concentrations ^{f)}				Х		Х	Х	Х	Х	X
Liver and spleen volumes ^{f)}				Х					Х	Х
Cardiac function ^{f)}				Х					Х	Х
Other clinical findings related to neurocognitive and behavioral changes										
12-lead electrocardiogram ^{f)}		Χ							Х	X
Cross-reactive immunologic material ⁱ⁾										—
AEs										—
Concomitant therapies/medications					Х	Х	Х	Х	Х	Х

- of JR-171.
- b) Vital signs: pulse rate, body temperature, blood pressure, respiratory rate, percutaneous oxygen g) saturation and body weight. During the infusion of JR-171, it is necessary to monitor other than body h) Anti-JR-171 antibodies weight (see Section 6.1 and 8.2.3).
- c) Excluding body weight
- d) Only body weight is measured.
- e) Perform before and after administration of JR-171 except for body weight. Body weight will be measured at either measuring point.
- a) Neurocognitive testing and adaptive behavior assessment will be performed before the first infusion f) Perform before administration of JR-171 (or before laronidase at Week 5, for subjects who will receive laronidase after completing the JR-171-101 study)
 - Anti-IDUA and anti-JR-171 antibodies

 - Blood specimens should be collected by following the "PK sampling schedule (plasma drug concentration)".
 - Performed within 5 hours after the end of administration of JR-171

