2.1 Study Rationale¹⁾

MPS I is an autosomal recessive disorder caused by a deficiency of IDUA, a lysosomal enzyme involved in the breakdown of GAGs, which results in systemic accumulation of GAGs, particularly DS and HS. The accumulation of GAGs causes various symptoms, including deafness, otitis media, bone or joint deformity, joint contracture, obstructive respiratory disorder, apnea syndrome, cardiac valvulopathy, and CNS symptoms. MPS I is classified into three forms based on age of onset, clinical manifestation, severity, and degree of disease progression: Hurler syndrome, which is the most severe form, and Hurler-Scheie syndrome and Scheie syndrome, which are milder than Hurler syndrome. The most severe form, Hurler syndrome, clinically manifests in early childhood and progresses rapidly. It has been reported that approximately 75% of naïve patients with Hurler syndrome die before 10 years of age due to obstructive respiratory disorder, respiratory infection, cardiac complications, etc. On the other hand, the mildest form Scheie syndrome initially manifests as heart valve disease, corneal opacity, joint contracture, hernia, carpal tunnel syndrome, etc., but these symptoms are mild or associated with other diseases, often leaving Scheie syndrome undiagnosed until adulthood. Patients with Hurler syndrome have CNS symptoms, whereas Scheie syndrome involves no CNS symptoms. Hurler-Scheie syndrome is of intermediate severity and involves only mild CNS symptoms or none at all.

MPS I is a very rare disease, with an estimated prevalence of 0.11-3.62 per 100000 live births. In particular, the prevalence in Japan, the US, and Brazil is estimated to be 0.23, 0.34, and 0.24 per 100000 live births, respectively.²⁾ A study of 987 patients with MPS I registered in the Global MPS I Registry reported that Hurler syndrome, Hurler-Scheie syndrome, and Scheie syndrome accounted for 60.9%, 23.0%, and 12.9% of patients, respectively (unknown in 3.2% cases).³⁾

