2.3.3 Assessment of Potential Risks and Benefits

Given its current battery of nonclinical studies results, JR-171 is expected to suppress central nervous and systemic symptoms of MPS I by being transported to the cerebral parenchyma via hTfR and to peripheral organ cells via M6PR and hTfR to decrease intracellularly accumulated GAGs. In addition, no safety concerns have been raised in the nonclinical studies that have been conducted to date.

3. Objectives and Endpoints

Objectives	Endpoints	Justification for endpoints
Primary		
To determine the safety and tolerability of JR-171 in patients with MPS I	 Frequency and severity of AEs and their relationship to JR-171 Changes in laboratory parameters (hematology, biochemistry, serum iron tests, and urinalysis) Changes in vital signs (pulse rate, body temperature, blood pressure, respiratory rate and percutaneous oxygen saturation) Clinically meaningful changes in 12-lead electrocardiogram Anti-drug antibody production (anti-human IDUA and anti-JR-171 antibodies) Frequency of IARs 	For safety endpoints, those which are commonly used (AEs, routine laboratory tests, vital signs, and 12-lead electrocardiogram) have been chosen. The determination of serum iron levels was included based on the involvement of hTfR, responsible for iron transport, in the mechanism of cellular uptake of JR-171. Given the possibilities of the administration of JR-171 leading to antibody production and occurrence of IAR, the antibody tests and IAR have been included. The antibody tests will measure anti-IDUA and anti-JR-171 antibodies.
Secondary		
To evaluate the plasma PKs of JR-171 after intravenous administration	Assessment of plasma drug concentrations and pharmacokinetic parameters	

Objectives	Endpoints	Justification for endpoints
Secondary (cont.)		
To explore the efficacy of JR-171 for CNS and somatic symptoms of MPS I		
	Changes in HS and DS concentrations in the CSF from baseline to Week 4 in Part 1 or Week 12 in Part 2	Given accumulation of HS and DS in patients with MPS I, this endpoint was selected to explore the efficacy of JR-171 on CNS symptoms.
	Changes in CSF opening pressure from baseline to Week 4 in Part 1 or Week 12 in Part 2	This endpoint was selected to explore the efficacy of JR-171 on CNS abnormalities.

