8.2.5 Antibodies

Antibodies will be measured centrally by the laboratory under contract with the sponsor. If the test results of anti-JR-171 antibodies are positive, then neutralizing activity against M6PR binding and hTfR binding of JR-171 will be measured.

Venous blood will be collected from each subject before administration of JR-171 or laronidase to measure anti-IDUA and anti-JR-171 antibodies. In the eCRF, whether or not a measurement has been performed and, if applicable, the sample collection date should be recorded. Data should be reported by the laboratory.

8.2.6 12-lead Electrocardiogram

Electrocardiography will be performed before administration of JR-171 or laronidase. In the eCRF, whether or not a measurement has been performed as well as the date of measurement and the presence or absence of abnormal finding, including its details and whether or not it will be considered an AE, should be recorded.

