9.4.3 Safety Analyses

This section outlines the planned safety analyses in the JR-171-101 study. Safety analyses will be performed on the SS.

All AEs will be coded to PT and system organ class (SOC) using the latest version of the Medical dictionary for regulatory activities terminology (MedDRA).

All AEs occurred after the first dose of JR-171 will be considered as treatment-emergent AEs and will be summarized by study period and dose group. For each study period and dose group, the incidence proportion of AEs will be summarized with frequency and percentage by MedDRA SOC and PT.

AEs occurring before the first dose of JR-171, include AEs that occurred in screen failure, will be pooled regardless study period or dose group and summarized in the same way.

For laboratory tests, summary statistics of measured values at each time point as well as changes from baseline will be calculated for Part 1 and each group in Part 2, and time courses

or shift tables will be created for each subject.

For vital signs, summary statistics of measured values at each time point as well as changes from baseline will be calculated for Part 1 and each group in Part 2, and time courses will be created.

For 12-lead electrocardiogram, the presence or absence of abnormality will be tabulated.

For antibody tests, shift tables will be created with respect to the presence or absence of antibody development at each time point.

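### The primary-objective ECG endpoint is a change, but the only stated ECG analysis is a tabulation of abnormality with no comparison to screening

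*Combined protocol and SAP*

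**What the plan says.** Sections 1.1 and 3 place the ECG endpoint under the primary objective of safety and tolerability, worded as "Clinically meaningful changes in 12-lead electrocardiogram". The analysis is in Section 9.4.3, in one sentence: "For 12-lead electrocardiogram, the presence or absence of abnormality will be tabulated".

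That section treats the neighbouring measures differently:

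- Laboratory tests and vital signs get summaries by time point and changes from baseline, for Part 1 and each Part 2 group.
- Laboratory tests also get time courses "or shift tables will be created for each subject".
- Antibodies, which like the ECG are a yes/no result, are handled this way: "shift tables will be created with respect to the presence or absence of antibody development at each time point".

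The Schedule of Activities (Section 1.3) places the ECG at screening and at Week 5 (Part 1) or Week 13 (Part 2), or at discontinuation. Section 8.2.6 says what the eCRF holds for each ECG: "the presence or absence of abnormal finding, including its details and whether or not it will be considered an AE, should be recorded".

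**The concern.** An abnormal ECG is a state at one visit. The endpoint is a change between visits. If the table only counts abnormal ECGs at each visit, it drops the link between a subject's two recordings, and equal counts before and after treatment could hide new abnormalities offset by resolved ones.

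The disease gives this some weight. Section 2.1 lists "obstructive respiratory disorder, apnea syndrome, cardiac valvulopathy, and CNS symptoms" among the manifestations of MPS I, and Section 8.5.7 attributes reduced cardiac function to heparan and dermatan sulfate accumulating in the heart. Some subjects may therefore enter with an abnormal ECG. The trial is open-label with no placebo group (Sections 4.2 and 6.3), so a subject's own pre-treatment recording is the main reference for judging whether a finding is new. What is at stake is whether this endpoint has a prespecified analysis that matches its wording.

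**Working it through.** The documents give no figure for the ECG endpoint, so there is nothing to reproduce. The check sets the text side by side and then works out what visit counts alone can show.

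**Text comparison**

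| Measure (Section 9.4.3) | Baseline comparison stated | Time point stated | Grouping stated |
|---|---|---|---|
| Laboratory tests | Yes | Yes | Yes |
| Vital signs | Yes | Yes | Yes |
| Antibodies | Yes (shift table) | Yes | No |
| 12-lead ECG | No | No | No |

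**Is a paired analysis possible?** Yes. Under Section 9.4.1.2, baseline is the last measurement before first dose. For the ECG this is the screening recording, the only scheduled one before dosing. The final recording is at Week 5, Week 13 or discontinuation. Section 8.2.6 captures the finding, its details and its AE status. The gap is in the stated analysis, not in data collection.

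**What visit counts can show**

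Let *n* be the subjects with both ECGs, *a* the number abnormal at screening and *b* the number abnormal at the final visit. The number of new abnormalities (normal at screening, abnormal at the end) lies between

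- lower bound: max(0, *b* − *a*)
- upper bound: min(*b*, *n* − *a*)

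Group sizes come from the documents: 4 in Part 1 (Section 9.2) and at least 6 per randomized group (Section 4.1). The abnormal counts are assumptions, because the documents give none.

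| *n* | *a* (assumed) | *b* (assumed) | Lower | Upper | New abnormalities |
|---|---|---|---|---|---|
| 4 | 2 | 2 | max(0, 0) = 0 | min(2, 2) = 2 | 0 to 2 |
| 6 | 3 | 3 | max(0, 0) = 0 | min(3, 3) = 3 | 0 to 3 |
| 6 | 2 | 3 | max(0, 1) = 1 | min(3, 4) = 3 | 1 to 3 |
| 6 | 0 | 2 | max(0, 2) = 2 | min(2, 6) = 2 | exactly 2 |

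For *n* = 6, half abnormal at both visits is the least informative case. With nobody abnormal at screening the ambiguity disappears, as the last row shows. Over all 7 × 7 = 49 possible pairs (*a*, *b*) for *n* = 6, the counts leave the number of new abnormalities undetermined in 25. For *n* = 4 it is 9 of 25. These are numbers of possible pairs, not probabilities.

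A shift table gives the number of new abnormalities exactly, whatever the counts.

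**Do the AE tables fill the gap?** In part. Appendix 2 (Section 10.2.1) makes an ECG abnormality an AE, including one that has worsened since consent, if the investigator judges it clinically significant. AEs after first dose are tabulated by study period and dose group (Section 9.4.3). The same appendix leaves out abnormalities associated with the underlying disease unless they are judged worse than anticipated for that subject. In MPS I, that is the category in which a change is hardest to classify.

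**The case against.** The strongest reply is that the sentence in Section 9.4.3 does not prescribe counts per visit. A screening-by-final cross-tabulation would also satisfy it, and Section 9.4 calls itself a summary, with a more detailed statistical analysis plan to follow. This stands. A reader might infer that the plan cannot separate new from pre-existing abnormalities, but the text supports only that it does not say it will. Against that, Section 9.4 says it covers the primary endpoints, it does specify shift tables elsewhere, and no supplied text contains an ECG change analysis.

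A second reply is that clinical meaningfulness needs clinical judgment, which is what the AE assessment supplies. This also stands in part. A reader might infer that the endpoint is not delivered at all, and that goes too far, since worsening judged clinically significant reaches the treatment-emergent AE tables. But AE frequency is a separately listed endpoint, and the underlying-disease exclusion limits this route.

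Third, a reader might infer that abnormal screening ECGs are common in these subjects. The documents do not say so. They describe valve disease and reduced cardiac function in MPS I and give no ECG abnormality rate. Plausible is as far as they go.

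Finally, groups this small can be read subject by subject. That is fair on severity, but Section 9.4.3 promises no ECG listing. The subject list in Section 9.4.1.4 is described only for cases with unscheduled measurements.

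**Conclusion.** The point holds as a mismatch between endpoint and stated analysis. The endpoint is a change, while the single ECG sentence specifies no comparison with screening, no time point and no grouping. The consequence depends on how the sentence is carried out. Under the counts-per-visit reading, new abnormalities could go unidentified, by up to 3 in a group of 6 under the assumed counts. Under a cross-tabulation reading, little would be lost beyond worsening in subjects already abnormal at screening.

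The severity is modest. Section 9.1 plans no hypothesis tests for safety, the groups are small, and the paired results remain in the eCRF. The change is still worth making, because a primary-objective endpoint should have a prespecified analysis that matches it and this one costs very little.

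**What to change.** Replace the ECG sentence in Section 9.4.3, and carry the same text into any separate statistical analysis plan:

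> For 12-lead ECG, shift tables (normal/abnormal, screening to Week 5 in Part 1 or Week 13 in Part 2, or discontinuation) will be created for Part 1 and each group in Part 2, in subjects who received JR-171 and have both ECGs. ECG findings that are new, or that differ from screening in subjects already abnormal, will be listed by subject with the recorded details and the investigator's AE assessment.

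The restriction to treated subjects with both ECGs is needed because the safety set in Section 9.3 is everyone who signs the consent form. Screen failures with only a screening ECG could otherwise enter the table. The listing is needed because a normal/abnormal shift table cannot show worsening in a subject who was already abnormal.

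The cost is one table and one listing from data already in the eCRF. Worsening is not a recorded field, so identifying it requires review of the recorded details. Neither output defines what counts as clinically meaningful; that remains a clinical judgment, which the listing would make visible.

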2.3 Benefit/Risk Assessment

2.3.1 Known Potential Risks

As JR-171 contains anti-hTfR antibody, the ordinary iron transport system (binding of transferrin to the transferrin receptor) might be inhibited, which may lead to the development of adverse drug reactions (anemia, etc.). JR-171 is also considered to cross the blood-brain barrier, and adverse drug reactions (vomiting, headache, etc.) may therefore occur. Furthermore, the enzyme portion of JR-171 is similar to laronidase, and similar adverse drug reactions reported with use of laronidase may occur, including those potential risks, anaphylactic shock, and IARs as well as anti-JR-171 antibody and anti-IDUA antibody production.

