4.2 Scientific Rationale for Study Design

JR-171 is expected to provide clinical benefit to MPS I patients especially those who show CNS manifestations. Since many patients with MPS I are receiving ERT⁸⁾ or/and have received an HSCT,⁵⁾ and it is very difficult to enroll naïve patients, the JR-171-101 study is designed to target MPS I patients with or without previous HSCT treatment and to mainly focus on the switch in treatment from laronidase to JR-171. Laronidase will be totally eliminated from the subject's body within 1 week because its mean t_{1/2} ranges from 1.5 to 3.6 hours. Moreover,

given that there is no evidence of accumulation of laronidase,⁷⁾ no extended washout period prior to switching from laronidase is included to evaluate the safety and exploratory efficacy of JR-171. Since interruption of ERT for MPS I over a certain period of time may result in irreversible progression of the disease, no placebo control group is included from an ethical perspective. The JR-171-101 study will be conducted, in part, to evaluate the safety of JR-171 and to explore its efficacy.

Since this is a first-in-human study of JR-171, in Part 1, four MPS I patients aged 18 years or older will receive 4 times JR-171 administration in a weekly dose-escalation manner. When it is concluded that there are no safety issues in Part 1 and JR-171 can be shown to potentially penetrate the blood-brain barrier in humans, treatment in Part 2 will be started in approximately 15 subjects with MPS I.

Since no accumulation of HS and DS is observed in non-MPS patients,^{9), 10)} and there are risks that the administration of protein drug to healthy volunteers, in terms of neutralizing antibody production, this phase I/II study is conducted in subjects with MPS I to assess the relationship between PKs and pharmacodynamics.

The nonclinical safety of JR-171 was demonstrated in a repeated intravenous dose toxicity study where male and female cynomolgus monkeys received JR-171 at a dosage of 40 mg/kg once a week for 4 weeks. Furthermore, a 13-week toxicity study will be completed before this phase I/II recruits subjects. Given a decrease in accumulated GAGs in the brain and other peripheral organs in a repeated intravenous dose study where hTfR KI/Idua KO mice received JR-171 once every week or once every 2 weeks for 12 weeks, the duration of the present study is considered to be appropriate to evaluate the efficacy in an exploratory manner.

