5.1 Inclusion Criteria

Patients are eligible to be included in the study only if all of the following criteria apply:

- 1. A patient aged 18 years or older in Part 1, or 2 years or older (any age in Japan and Brazil) in Part 2, at the time of informed consent.
- 2. A patient from whom written informed consent can be obtained. If the patient is aged under 18 years (20 years in case of Japan) at the time of assent or willingness to participate in the study cannot be confirmed due to MPS I-related intellectual disability, informed permission from the patient's legally acceptable representative (e.g., his/her parents or guardians) needs to be obtained instead of his/her consent. Even in this case, written informed consent should be obtained from the patient, wherever possible.
- 3. A patient diagnosed with MPS I based on any one of the following criteria:
 - Activity of the IDUA enzyme below 10% of the lower reference level in leucocytes or cultured skin fibroblasts, AND increased age-related urinary levels of GAGs (before ERT).
 - Activity of the IDUA enzyme below 10% of the lower reference level in leucocytes or cultured skin fibroblasts, AND presence of one pathogenic mutation in each of the alleles of the IDUA gene.
 - Increased age-related urinary levels of GAGs (before ERT), AND presence of one pathogenic mutation in each of the alleles of the IDUA gene.
- 4. A patient diagnosed as having mild or no MPS I-related intellectual disability (able to report their own subjective symptoms) by the principal investigator or subinvestigator (Part 1 only).
- 5. A patient who has received laronidase continuously for at least 12 weeks and has received laronidase at a stable dosage for the 2 weeks immediately before the initial administration of JR-171 (except for a laronidase naïve patient or a patient who has previously been treated by HSCT).
- 6. Female patient or male patient whose co-partner is of child-bearing potential agrees to use a medically accepted, highly effective method of contraception, such as spermatocidal gel plus condom, an intrauterine device or oral contraceptives until one month after the final administration.

Rationale for the Inclusion Criteria:

- 1. In this first in human study of JR-171, the minimum age of 18 years was defined in Part 1 for safety considerations. In Part 2, pediatric patients will be also eligible to participate since treatment of MPS I often starts in childhood.

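### Anti-drug antibody production sits under the primary objective, but its only stated analysis, a presence/absence shift table, cannot show a rise in subjects already antibody-positive at baseline

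*Combined protocol and SAP*

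**What the plan says.** Section 3 (Objectives and Endpoints) lists, under the primary safety objective, "Anti-drug antibody production (anti-human IDUA and anti-JR-171 antibodies". Section 9.4.3 gives that endpoint one sentence: "For antibody tests, shift tables will be created with respect to the presence or absence of antibody development at each time point". It mentions no titre or level, no change from baseline, and no rule separating antibody induced by JR-171 from antibody boosted by it. Elsewhere in 9.4.3, laboratory tests and vital signs are handled quantitatively: "summary statistics of measured values at each time point as well as changes from baseline will be calculated for Part 1" and for each group in Part 2.

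On the population, Section 4.2 says the study is designed "to mainly focus on the switch in treatment from laronidase to JR-171". Inclusion criterion 5 in Section 5.1 requires "A patient who has received laronidase continuously for at least 12 weeks", with exceptions for laronidase-naive patients and patients with a previous transplant. Section 2.3.1 states that "the enzyme portion of JR-171 is similar to laronidase" and names "anti-JR-171 antibody and anti-IDUA antibody production" among the potential risks. Section 2.2 describes JR-171 as IDUA joined to the Fab fragment of an anti-transferrin-receptor antibody.

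Section 8.2.5 has antibodies measured centrally. Samples positive for anti-JR-171 are then tested for neutralising activity against M6PR and hTfR binding. Section 9.4.3 has no analysis of that activity.

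**The concern.** The endpoint is antibody production. In a subject who starts negative, production is a change from absent to present, and a shift table records it. In a subject who starts positive, production is an increase in amount, and a present/absent table has no cell for it. Such a subject can only be shown as unchanged or as having become negative.

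This matters because many subjects will have been treated with a closely related enzyme before the first dose of JR-171. Some may carry antibody to the enzyme part. If that antibody also registers in the anti-JR-171 assay, a new response to the Fab part, which laronidase does not contain, would be hidden in the same way.

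No hypothesis test is planned for safety (Section 9.1), so the descriptive table is the whole antibody result. Without a level, the report has nothing to set beside infusion reactions or reduced plasma exposure, to which antibody is a plausible contributor.

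**Working it through.** **1. No figure to reproduce.** No rate, power or test is attached to the antibody endpoint, and Section 9.2 bases both sample sizes on feasibility. The check is therefore of what the table can show.

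**2. What each course looks like in the table.**

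| Baseline | What happens on JR-171 | Cell |
|---|---|---|
| Negative | Becomes positive | Negative to positive |
| Positive | Level unchanged | Positive to positive |
| Positive | Level rises | Positive to positive |
| Anti-JR-171 positive through the enzyme part | New response to the Fab part | Positive to positive |
| Positive | Becomes negative | Positive to negative |

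Three different courses share one cell. This follows from the form of the table and needs no assumed rate.

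**3. Can baseline positivity arise?** The documents support the possibility: prior laronidase for most switched subjects (5.1, 4.2), a similar enzyme (2.3.1), and antibody production as a named risk (2.3.1). They do not state that laronidase-treated patients are positive, or that the anti-IDUA and anti-JR-171 assays cross-react. Both antibodies are measured at baseline (Section 1.3), so positivity would be seen in the data.

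**4. Illustration only.** Let π be the share positive at baseline; this is an assumption, since the documents give no value. In a group of n, the expected number able to show a negative-to-positive shift is n(1 − π), and the chance that nobody can is π^n, taking subjects as independent. Group sizes are at least 6 per randomised arm (Section 4.1) and 4 in Part 1 (Section 9.2).

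| π | n = 6: expected | n = 6: none | n = 4: expected | n = 4: none |
|---|---|---|---|---|
| 25% | 4.5 | <0.1% | 3.0 | 0.4% |
| 50% | 3.0 | 1.6% | 2.0 | 6.2% |
| 75% | 1.5 | 17.8% | 1.0 | 31.6% |
| 90% | 0.6 | 53.1% | 0.4 | 65.6% |

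For example, 6 × (1 − 0.75) = 1.5 and 0.75^6 = 0.178.

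These figures apply π to every member of the group. If instead 2 of the 6 have never had laronidase and are negative (also an assumption), the expected number is 2 + 4(1 − π). That gives 5.0, 4.0, 3.0 and 2.4 for the four values of π, and the chance of none is 0. The size of the loss thus depends on the mix of exposed and unexposed subjects, which is not known.

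**5. What the schedule allows (Section 1.3).** Anti-JR-171 is sampled at baseline, Week 2 and Week 5 in Part 1, and at baseline and Weeks 2, 4, 8 and 13 in Part 2. Anti-IDUA is sampled only at baseline and Week 5 (Part 1) or Week 13 (Part 2). Both are also sampled at discontinuation. Fold change can therefore be followed over visits for anti-JR-171, but for anti-IDUA there is a single scheduled post-baseline value. Plasma drug concentration in the randomised groups is taken at Weeks 1, 4 and 12. Week 4 has a matching anti-JR-171 sample; Week 12 does not, and the nearest is Week 13.

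**The case against.** Section 9.4 calls itself a summary and says that the statistical analysis plan will give more technical detail. Section 9.4.3 likewise describes itself as an outline. No such separate plan is in the supplied text, so it may already contain titres. The laboratory may already report levels, since Section 8.2.5 does not say what the assay yields. The word development in 9.4.3 is undefined and could be meant to cover boosting. Section 9.4.1.4 refers to subject lists of measurements, which might include antibody levels.

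These points limit how far one can say that titres are absent from the whole plan. They do not make the stated method adequate. Section 9.4 says it covers the most important endpoints, including the primary ones, so the antibody method belongs there. No rule in the text defines boosting.

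A reader might infer that the table counts only baseline-negative subjects and would read as little or no antibody production. The documents do not support that: the table shows every subject, and the number already positive at baseline is visible.

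A reader might also infer that most subjects will be positive at baseline. No figure supports this. Groups may include laronidase-naive and transplanted subjects (Sections 5.1 and 6.3), and Sections 9.4.5.3 and 9.4.5.8 provide for 3 or more naive subjects in a dose group.

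Nor do the documents make antibody the most likely explanation of infusion reactions or falling exposure. Infusion reactions are a primary endpoint in their own right, and Section 9.4.4 gives plasma concentration listings and time courses per subject, so neither is hidden. What is missing is an antibody level to relate to them.

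**Conclusion.** The point holds in a limited form. For any subject positive at baseline, the stated analysis cannot distinguish a stable antibody level from a rise. For anti-JR-171 it also cannot show a new response to the Fab part in a subject already positive through the enzyme part. That loss is complete for those subjects and does not rest on an assumed rate.

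How many subjects are affected is unknown. The calculations above illustrate sensitivity to an assumed share and are not an estimate for this trial. Laronidase-naive subjects, and transplanted subjects without laronidase exposure, are less affected.

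The conclusion rests on two things: that some switched subjects are positive at baseline, which is plausible but not stated, and that the supplied text is the operative description of the analysis. The change should be made because the endpoint is under the primary objective and the better analysis is cheap. It has no bearing on sample size, because the endpoint is descriptive.

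**What to change.** In Section 8.2.5, state that the contracted laboratory reports a titre, or a semi-quantitative level, for every positive anti-IDUA and anti-JR-171 sample already scheduled.

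In Section 9.4.3, keep the shift table and add:

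- titre and fold change from baseline for each subject at the scheduled antibody visits: anti-JR-171 at all of them, anti-IDUA at baseline and Week 5 (Part 1) or Week 13 (Part 2), or discontinuation;
- counts of treatment-induced subjects (negative to positive) and treatment-boosted subjects (positive at baseline with a rise above a fold threshold fixed in advance from assay precision);
- results split by baseline antibody status;
- neutralising activity against M6PR and hTfR binding in anti-JR-171-positive samples, tabulated by visit. The hTfR result may help to reveal a response to the Fab part.

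If a separate analysis plan already contains these items, a sentence in 9.4.3 pointing to them is enough.

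The cost is added assay and reporting work. No new visits are needed. Whether titration needs more sample volume cannot be checked, because the volumes in Section 10.1.8 are not shown.
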